Therapeutic Effects of Topical Herbal Medicine -Rhubarb Ointment on Rosacea

NCT number: NCT05045469

document date:2025/03/12

Study Aims

A review of the literature reveals that clinical studies on topical botanical and traditional Chinese herbal medicine (TCM) for rosacea are limited. A 2012 study published in The Journal of Clinical Pharmacology reported that Quassia extract significantly improved erythema, flushing, papules, and vascular proliferation in rosacea patients. Additionally, a 2005 randomized trial published in the European Academy of Dermatology and Venereology demonstrated that chrysanthemum extract was more effective than the control group in reducing erythema area and severity.

Currently, the optimal treatment for rosacea remains unclear, and research on the therapeutic effects of topical Chinese herbal medicine for rosacea is scarce. According to the Qing Dynasty medical classic Yi Zong Jin Jian, the Diandao San formula, which contain rhubarb is traditionally used to clear heat, eliminate parasites, detoxify, cool the blood, and promote blood circulation, making it suitable for treating conditions such as erythema, acne, and folliculitis, which align with rosacea symptoms.

Recent studies also suggest that combination therapy is beneficial in treating rosacea. Therefore, this study aims to evaluate the efficacy of this TCM herbal formula in the treatment of rosacea.

IRB number: 202101000A3

Study Design

Patients were enrolled in the study following assessment by dermatologists or traditional Chinese medicine (TCM) practitioners, ensuring they met the inclusion and exclusion criteria.

Inclusion Criteria:

- Patients aged 20 years or older diagnosed with rosacea.
- Willing to sign a written informed consent form and comply with medical guidance.
- No use of any medication for rosacea treatment within the past two weeks.

Exclusion Criteria:

- History of malignant skin tumors at the rosacea-affected site.
- High risk of skin infection at the affected site.
- History of allergic reactions to topical herbal medicines.
- Pregnant individuals.
- Inability to complete study questionnaires or comply with medical instructions.

The study enrolled 24 participants from two sites: Keelung Hospital and Lover's Lake Hospital. Participants were randomly assigned into two groups via computer-generated randomization, with 12 individuals in the experimental group and 12 in the control group. The experimental group received *Diandao San* ointment, while the control group received a placebo ointment with a similar appearance and scent but without therapeutic effects. Both ointments were applied twice daily to clean skin on the affected areas for six weeks. In cases of adverse skin reactions, application was temporarily halted, and the reactions were documented and monitored.

Assessment and Evaluation

Before enrollment, participants underwent evaluations, including Fitzpatrick skin type classification, distribution of rosacea lesions, severity of erythema, papules, and pustules, and quality of life assessments. Adverse skin reactions were also recorded. Follow-up assessments were conducted at weeks 1, 2, 4, and 6 by TCM practitioners, who re-evaluated skin symptoms, quality of life, and adverse reactions.

- **Skin Type:** Assessed using the Fitzpatrick classification scale.
- **Lesion Distribution:** Documented with photographs, noting affected areas such as bilateral cheeks, nose, chin, forehead, and eyes.
- **Severity of Skin Symptoms:** Assessed using the Investigator Global Assessment (IGA) scale.
- **Quality of Life:** Measured using the Dermatology Quality of Life Index (DQoL), evaluating emotional, symptomatic, and lifestyle impacts.

Participants in the experimental group achieving an IGA and DQoL score of 0-1 after six weeks were considered to have significant improvement and did not require further treatment. Those with IGA scores of 2-3 or DQoL scores between 2-10, showing significant improvement compared to baseline, continued using *Diandao San* ointment. Participants with no significant improvement post-trial were referred to dermatologists and TCM practitioners for alternative treatment options. In the control group, participants experiencing severe adverse reactions, allergic responses, or infections were immediately withdrawn from the study and evaluated for further treatment.

Data Analysis

Statistical analysis was performed using SPSS software. Baseline differences were analyzed using ANOVA, while paired t-tests were used to compare pre- and post-treatment data. The study assessed all parameters, including mean values and standard deviations, with a significance level set at $\alpha = 0.05$ (one-tailed).

The analysis uses Robust Linear Mixed-Effect Models (LMMs) due to the violation of normality in outcome measurements. To address this issue, robust LMM was applied to enhance the reliability of estimates by mitigating the effects of outliers or non-normal data distributions.

Additionally, the robustlmm method was used, which down-weights outliers by modifying the loss function, ensuring that extreme observations do not disproportionately influence the fixed effect estimates. This approach increases the robustness of estimation methods, improving the accuracy and stability of the results.

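### The rule withdrawing patients after a severe reaction, allergy or infection is written for the control arm only, so follow-up lost through it falls on one arm

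*Combined protocol and SAP*

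**What the plan says.** Two rules deal with reactions during treatment.

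The first is in the treatment paragraph of Study Design. It names no arm and follows a sentence about both products ("Both ointments were applied twice daily to clean skin on the affected areas for six weeks"). It reads: "In cases of adverse skin reactions, application was temporarily halted, and the reactions were documented and monitored". This pauses dosing; it does not end participation.

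The second is in the last paragraph of Assessment and Evaluation and is restricted to one arm: "In the control group, participants experiencing severe adverse reactions, allergic responses, or infections were immediately withdrawn from the study". The sentence goes on to say that these patients were assessed for further care.

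The only rule in that paragraph written specifically for Diandao San patients concerns response at the end of treatment. It begins "Participants in the experimental group achieving an IGA and DQoL score of 0-1 after six weeks were considered to have significant improvement" and goes on to who continues the ointment. The referral of patients without improvement names no arm and is not a safety rule.

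On follow-up: "Follow-up assessments were conducted at weeks 1, 2, 4, and 6 by TCM practitioners". On analysis, Data Analysis says that "paired t-tests were used to compare pre- and post-treatment data" and that "The analysis uses Robust Linear Mixed-Effect Models (LMMs) due to the violation of normality in outcome measurements". It defines no analysis set and does not say how withdrawn patients are handled.

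**The concern.** In a randomised comparison, the same clinical event should have the same consequence for follow-up in both arms. Here a severe reaction, an allergy or an infection removes a placebo patient from the study, while the only rule that reaches a Diandao San patient is a pause in application.

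Two things are at stake.

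- **Comparison of arms.** Missing data produced by this rule can arise in the control arm only, and they arise because of the patient's skin condition, which is what the trial measures. A withdrawn control has no week-6 value for the paired t-test. The mixed model can still use visits before withdrawal, but its week-6 estimate then rests on an assumption about what would have followed the event.
- **Safety rule.** The Exclusion Criteria list "History of allergic reactions to topical herbal medicines", so the plan itself treats allergy to herbal products as a risk. Yet a new allergy to the herbal ointment under test has no written permanent stop, while the same event on placebo ends participation.

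**Working it through.** The plan gives no event rate, withdrawal count, SD or sample-size derivation, so it has no figure of its own to reproduce.

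**Inputs from the plan:** 12 patients per arm (Study Design); scores at baseline and weeks 1, 2, 4 and 6 (Assessment and Evaluation); one-sided 0.05 (Data Analysis).

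**Assumptions:** event rate p of 5%, 10% or 20% among controls; scores scaled to unit SD; correlation 0.6 between visits; a worsening of 1.5 SD at the event.

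**Step 1. Withdrawals by rule.** The expected number of controls withdrawn is 12p, and the chance of at least one is 1 − (1 − p)^12. The number required by rule under Diandao San is 0.

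**Step 2. Shift in the observed control mean.** If k withdrawn controls would have scored x points away from the remaining controls at week 6, including them moves the control mean by kx/12.

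- k = 1, x = 1 to 3 IGA points: 1/12 = 0.083 to 3/12 = 0.250.
- k = 2, x = 1 to 3: 2/12 = 0.167 to 6/12 = 0.500. The upper end is an extreme case: it needs two withdrawn controls, each 3 points away, and the plan mentions IGA scores of 0 to 3 only.

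**Step 3. Bias in a mixed model that uses visits before withdrawal.** This was simulated with 400,000 controls per setting, a random intercept, and visit means by generalised least squares. The event falls at a random follow-up visit, which is scored; later control visits are missing. Bias is the change in the estimated week-6 benefit compared with scoring everyone. A negative value means that the benefit of Diandao San is understated.

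| p | 12p | P(at least one) | Bias if worsening persists to week 6 (SD) | Bias if it resolves after the event visit (SD) |
|---|---|---|---|---|
| 5% | 0.6 | 0.460 | −0.040 | +0.018 |
| 10% | 1.2 | 0.718 | −0.077 | +0.036 |
| 20% | 2.4 | 0.931 | −0.145 | +0.081 |

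The sign changes for a simple reason. If the worsening would have lasted, withdrawal removes poor week-6 control scores. If it would have cleared, the model carries a temporary bad score forward to week 6.

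With correlation 0.4 to 0.8 and worsening of 1 to 2 SD, p = 20% gives −0.09 to −0.21 (persisting) and +0.05 to +0.12 (resolving). The simulated model is not robust. The planned fit down-weights outlying scores, and that was not simulated.

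**Step 4. Scale.** The standard error of a simple week-6 difference is sqrt(1/12 + 1/12) = 0.408 SD. The biases in the table are therefore between 0.018/0.408 = 4% and 0.145/0.408 = 36% of one standard error.

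**Step 5. Power.** At an assumed true effect of 1 SD and one-sided 0.05, power is 0.789 with 12 v 12 and 0.755 with 12 v 10. Lost power is minor; the issue is missingness that depends on arm.

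**The case against.** The strongest reply is that this is a drafting gap. The sentences around the rule describe what happens to patients after six weeks, and the rule itself ends with assessment for further care. It can be read as the control-arm half of a paragraph about care. Silence about Diandao San does not mean that its patients stayed in after a severe reaction. If the rule was meant for both arms and applied that way, the bias described here did not occur. This stands as a plausible reading. The documents cannot settle it, which is why confirmation comes first in the fix.

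Three further objections stand in part.

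- The paired t-test, as described, compares scores before and after treatment within patients. Lost control pairs weaken that comparison and do not act directly on the comparison between arms.
- Every magnitude rests on assumed rates, and nothing in the plan supports a rate as high as 20%. The bias is below one standard error throughout the ranges examined.
- The text is in the past tense, so continued scoring can no longer be put into practice if the conduct it describes is complete. Confirmation, reporting and sensitivity analysis remain possible.

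The pause that applies to both ointments does not answer the point, because a pause leaves the patient in follow-up and a withdrawal does not.

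A reader might infer more than the text supports. It does not show that all dropout depends on arm: missed visits, withdrawn consent and discretionary stops are not described for either arm. It does not show that Diandao San patients with severe reactions were in fact kept on treatment; nothing forbids withdrawing them. Nor does it show a bias in favour of Diandao San, since the sign depends on how the reactions would have evolved.

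**Conclusion.** The point holds in a limited form. As written, loss of follow-up caused by this rule can occur in the control arm only, and an allergy to Diandao San has no written permanent stop. This is a defect in a stated rule, and it should be corrected.

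The size and sign of any bias are unknown. Under the assumptions listed (5% to 20% event rate, 1.5 SD worsening, correlation 0.6) it is about 0.02 to 0.15 SD, against a standard error of about 0.41 SD. That is not enough to say that the result is wrong, but a reader of a trial with 12 per arm, where each patient is 8.3% of an arm, needs to know whether it happened. Confidence is medium, because a drafting slip would remove the problem.

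**What to change.** 1. Confirm whether the withdrawal rule was applied to both arms or to controls only.
2. Report withdrawals and permanent stops of ointment by arm, with reasons.
3. Replace the sentence with one rule for both arms: a severe reaction, allergy or infection stops the assigned ointment, the patient is still scored through week 6, and analysis is by assigned arm. Clinical care after the event is for the investigators to decide.
4. Only if controls alone were withdrawn, add a sensitivity analysis that includes them under stated assumptions, for example the last score and the worst score.

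The cost is one confirmation, one corrected sentence and one table, plus two further runs of the same model if step 4 applies. Rewording cannot change conduct already completed. The downside of continued scoring is that scores after stopping reflect partial treatment, though by rule equally in both arms.

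### The plan never states the ointment-versus-placebo comparison: its only written outcome contrast is a pre/post paired t-test, and the robust mixed model has no stated terms, outcome or arm contrast

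*Combined protocol and SAP*

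**What the plan says.** The Study Aims section gives the aim as evaluating the efficacy of the herbal formula in rosacea. Study Design describes a randomised trial "with 12 individuals in the experimental group and 12 in the control group", in which "the control group received a placebo ointment with a similar appearance and scent but without therapeutic effects". Follow-up visits are at weeks 1, 2, 4 and 6, and the ointments are applied for six weeks.

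The Data Analysis section names three methods, with a one-tailed significance level of 0.05:

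- **ANOVA**, for baseline only: "Baseline differences were analyzed using ANOVA".
- **Paired t-tests**, within participant: "paired t-tests were used to compare pre- and post-treatment data".
- **A robust linear mixed model**: "The analysis uses Robust Linear Mixed-Effect Models (LMMs) due to the violation of normality in outcome measurements". The rest of its description concerns how outliers are down-weighted, "ensuring that extreme observations do not disproportionately influence the fixed effect estimates".

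No outcome is singled out: "The study assessed all parameters, including mean values and standard deviations". The severity scale (IGA) and the quality-of-life index (DQoL) are both candidates.

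**The concern.** Randomisation protects one comparison, ointment against placebo. A pre/post change in a single arm combines any drug effect with the effect of the vehicle, natural fluctuation of the disease and regression to the mean. The placebo arm exists to remove these, and a paired t-test makes no use of it.

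The mixed model could make the arm comparison, but a mixed model is a class of models. An arm main effect over all visits, an arm difference at week 6, and a visit effect within the ointment arm all fit the description given, and they answer different questions. The last of them is the pre/post contrast again. With two unranked outcomes and four follow-up visits, a reader cannot tell which number decides efficacy, or whether that number is a between-arm difference at all.

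**Working it through.** **Text check.** The plan gives no sample-size calculation, SD or effect size, so it has no figure to reproduce. Each method in Data Analysis is set against what an arm comparison needs:

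| Method named | Outcome named | Arm contrast stated | Visit stated |
|---|---|---|---|
| ANOVA | baseline differences only | not for an outcome | baseline |
| Paired t-test | none singled out | no | pre and post only |
| Robust mixed model | none singled out | no | no |

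Nothing says whether the mixed model replaces, supplements or checks the paired tests. The end-of-trial categories in Assessment and Evaluation do not fill the gap. The first is written for the active arm alone ("Participants in the experimental group achieving an IGA and DQoL score of 0-1 after six weeks were considered to have significant improvement"), the next is judged against baseline, and both lead to decisions about further care.

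**Illustration of what is at stake.** Two things are assumed. First, efficacy is read from the ointment-arm paired t-test, a rule the documents do not state. Second, both arms improve by the same d SDs of change, so there is no drug effect. From the documents: n = 12 per arm and one-tailed α = 0.05.

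The paired test has df = 11 and critical value 1.796. Its rejection probability is P(T > 1.796), with T non-central t and non-centrality d√12.

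| d | d√12 | Paired test significant |
|---|---|---|
| 0.25 | 0.866 | 0.203 |
| 0.50 | 1.732 | 0.492 |
| 0.75 | 2.598 | 0.785 |
| 1.00 | 3.464 | 0.945 |

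Data Analysis says the outcomes were not normal, so the check was repeated by simulation (400,000 trials per setting, same distribution of change in both arms):

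| Distribution of change | d = 0.25 | 0.50 | 0.75 | 1.00 |
|---|---|---|---|---|
| Normal | 0.202 | 0.491 | 0.785 | 0.944 |
| Gamma, skewness +1.41 | 0.135 | 0.480 | 0.885 | 0.997 |
| Gamma, skewness −1.41 | 0.289 | 0.536 | 0.752 | 0.889 |
| t with 5 df, scaled to SD 1 | 0.224 | 0.538 | 0.804 | 0.935 |
| Normal, rounded to whole steps | 0.197 | 0.467 | 0.756 | 0.928 |

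A one-sided two-sample t-test between the arms rejected in 0.0489 to 0.0504 of trials across all settings. In the last row the SD is 1 step before rounding; rounding raises it to about √(1 + 1/12) = 1.04, so the effective d is about 4% below its label.

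Reading both arms' paired tests side by side is no cure. If p is the rejection probability above, ointment significant and placebo not has probability p(1 − p). At d = 0.5 this is 0.492 × 0.508 = 0.25, against a nominal 0.05.

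**Precision of the between-arm difference** (two-sample approximations to the mixed-model contrast, in SDs of change):

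- Unadjusted, df = 22: 90% half-width 1.717 × √(2/12) = 0.70; 95% half-width 2.074 × √(2/12) = 0.85.
- Baseline-adjusted, df = 21, equal variances, assumed baseline-to-week-6 correlation r. The residual variance σ²(1 − r²) replaces the change variance 2σ²(1 − r), so the SD is multiplied by √((1 + r)/2). For r = 0.3, 0.5 and 0.7 the factor is 0.806, 0.866 and 0.922. The 90% half-widths are 0.57, 0.61 and 0.65; the 95% half-widths are 0.68, 0.74 and 0.78. Chance baseline imbalance is ignored.

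**The case against.** The strongest reply is that the mixed model is the outcome analysis. The plan introduces it as the analysis, gives non-normality as the reason, and refers to fixed effects. In a randomised placebo-controlled trial with repeated visits, an arm term would be the natural inclusion. On that reading the defect is an incomplete model description, and one added sentence would cure it. This may well be what happened, and it is why the finding is that the comparison is unstated, not that it was never made. But the text does not settle the matter, and the only outcome contrast it spells out is one that cannot show efficacy.

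Three further points stand in part:

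- The error rates depend on a decision rule and a shared improvement that the documents do not contain. They show what is at risk if efficacy rests on within-arm change; they do not measure this trial's error rate.
- The 5% comparator is a two-sample t-test. The error rate of a robust mixed model in 24 participants was not simulated.
- The end-of-trial categories govern subsequent care and are not offered as endpoints. They say nothing about how the analysis was done, only that they do not supply the missing contrast.

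None of these supplies an ointment-minus-placebo comparison.

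**Conclusion.** The concern holds and must be fixed. In a placebo-controlled efficacy trial the treatment contrast is the item an analysis plan cannot omit, and here neither the contrast nor the outcome and visit it applies to is written down. That conclusion rests on the text alone and needs no assumption.

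The size is conditional. If efficacy were judged by the ointment-arm paired test, a shared improvement of half an SD of change would produce a false positive in about half of trials (47% to 54% across the distributions tried). If an arm contrast from the mixed model already decides efficacy, those rates do not apply and the defect is only that the contrast is unstated.

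**What to change.** State the mixed model that was fitted and the arm contrast that decides efficacy. Unless a different model was fitted, a suitable specification is:

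- **Model:** robust linear mixed model with baseline score, arm, visit and arm-by-visit as fixed effects and participant as random effect, in all randomised participants.
- **Deciding contrast:** ointment minus placebo at week 6, the end of the application period.
- **Outcome:** one of IGA or DQoL, according to what was originally approved.
- **Reporting:** the estimate, the direction tested and a 90% confidence interval, which matches the one-tailed 0.05, with an account of how the interval is obtained from a robust fit in 24 participants.
- **Paired t-tests:** say that the mixed model replaces them for inference, and report within-arm changes as descriptive only.

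If a different mixed model was fitted, write out that model and its arm contrast instead.

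The cost is stating or re-running one model and one contrast, with no new data. The document is dated 2025/03/12 and written in the past tense, so a contrast or outcome settled now may have to be labelled post hoc; say so if it was chosen after data were seen. The between-arm result may be less favourable than the pre/post result, and with 12 per arm its interval will be wide.

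### The one outcome comparison spelled out is a pre-post paired t-test, which cannot separate ointment from placebo; the robust mixed model is given no terms or between-arm contrast, and nothing says which analysis decides efficacy

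*Combined protocol and SAP*

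**What the plan says.** All statements are in the combined protocol and SAP.

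- **Design (Study Design).** Participants were randomised to Diandao San or placebo ointment, "with 12 individuals in the experimental group and 12 in the control group". On duration: "Both ointments were applied twice daily to clean skin on the affected areas for six weeks". IGA and DQoL were assessed before enrolment and at weeks 1, 2, 4 and 6 (Assessment and Evaluation).
- **Tests (Data Analysis).** ANOVA is assigned to baseline differences only. For outcomes, "paired t-tests were used to compare pre- and post-treatment data". The level is one-tailed 0.05 and is attached to everything measured: "The study assessed all parameters, including mean values and standard deviations, with a significance level set at" that value.
- **Model (Data Analysis).** "The analysis uses Robust Linear Mixed-Effect Models (LMMs) due to the violation of normality in outcome measurements". The rest of the description concerns the down-weighting of outliers, "ensuring that extreme observations do not disproportionately influence the fixed effect estimates". No response variable, fixed effect, visit or contrast is named.
- **Improvement categories (Assessment and Evaluation).** "Participants in the experimental group achieving an IGA and DQoL score of 0-1 after six weeks were considered to have significant improvement" and needed no further treatment. The next two sentences cover intermediate scores with improvement from baseline, and participants without improvement; neither names an arm. Together they decide care after the trial.

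No section names a primary outcome, a decision visit or a multiplicity rule.

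**The concern.** A paired pre-post test compares participants with themselves. It responds to anything that moves scores between baseline and week 6: a fluctuating disease entered at a bad moment, regression to the mean, the ointment base, or the attention of a trial. A placebo arm is there to remove these, and it does so only if the efficacy test uses it. If the paired test were taken as the efficacy test, a gain shared by both arms could be reported as an effect of the herbal ointment.

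The mixed model could supply the missing comparison, but its description does not say that it does. A group effect averaged over visits, a difference in slope and a week-6 difference in change answer different questions and can disagree. The text does not say which was tested, or whether model or t-test decides.

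A second, smaller matter is that two scales are assessed and neither is ranked. If significance on either may count, the chance of a false efficacy conclusion exceeds 5%.

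**Working it through.** The document gives no power calculation, effect size, SD or correlation, so there is no derived figure to reproduce; 12 + 12 = 24 agrees with the stated enrolment. The figures below size the consequence under stated assumptions.

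**Inputs from the document:** 12 per arm; one-tailed α = 0.05; two scales (IGA, DQoL); last visit week 6.

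**Assumptions:** the tested direction is improvement; the paired test is run within each arm (the text does not say); changes are roughly normal; shared improvement d = 0.3, 0.5 or 0.8 SD of change; correlation between scales 0.2 to 0.6.

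**1. Paired t-test in the ointment arm, no ointment effect.** Both arms improve by the same d. The statistic is noncentral t with 11 df and noncentrality d√12; the critical value is t(0.95, 11) = 1.796. With p the chance that one arm is significant, the pattern of ointment significant and placebo not has probability p(1 − p).

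| d (assumed) | d√12 | p, ointment arm significant | p(1 − p) |
|---|---|---|---|
| 0.3 | 1.04 | 0.252 | 0.188 |
| 0.5 | 1.73 | 0.492 | 0.250 |
| 0.8 | 2.77 | 0.829 | 0.142 |

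The last column also shows that reading the two arms' paired tests side by side does not repair the problem.

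If the paired test instead pools all 24 participants, the p(1 − p) column does not apply. The chance of significance with no ointment effect then uses 23 df and noncentrality d√24 (1.47, 2.45, 3.92), giving 0.41, 0.77 and 0.98.

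**2. Between-arm test of change, same situation.** The shared d cancels in the difference between arms. In simulation (200,000 trials per setting) the two-sample t-test was significant in 5.0% to 5.1% of trials, whatever the shared change.

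**3. Two scales, between-arm tests at week 6, no effect.** A two-sample t-test with 22 df (critical value 1.717) stands in for the model contrast. Since each test has a 5% rate, P(either) = 10% − P(both).

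| Correlation (assumed) | P(both), simulated | P(either) |
|---|---|---|
| 0.2 | 0.5% | 9.5% |
| 0.4 | 0.9% | 9.1% |
| 0.6 | 1.5% | 8.5% |

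If the scales were independent, P(either) = 1 − 0.95² = 9.75%.

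**4. Power of the between-arm contrast.** For an assumed difference of 0.8 SD, noncentrality is 0.8√6 = 1.96 with 22 df, which gives power 0.60 at one-sided 0.05. Power of 80% would need a difference of about 1.05 SD.

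**The case against.** The strongest reply is that the mixed model is the main analysis. It is introduced because normality failed, which reads as a reason for moving away from t-tests, and a model for a two-arm randomised trial would ordinarily carry a treatment term. On that reading the 25%, 49% and 83% describe a test that nobody would use for efficacy. This largely stands as to likelihood: those figures apply only if the paired test decides. It does not settle the matter, because no model term is named, the paired tests are still listed as performed, and neither analysis is given precedence.

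Three stronger readings are tempting and are not supported:

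- **That no between-arm analysis was done.** The document shows only that none is described. The model may already contain a group or group-by-time term.
- **That success was defined for the ointment arm alone.** Only the sentence on scores of 0-1 names the experimental group; the sentences on intermediate scores and on non-improvers name no arm. The whole passage is a post-trial care rule, not an endpoint.
- **That no primary outcome was ever fixed, or that an invalid claim was made.** A designation may exist in a source not available here, and the document reports no results.

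It is also fair to say that the sizes rest on assumed changes and correlations, and that a t-test at week 6 only approximates a robust model using all visits. The direction of both effects does not depend on those choices.

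**Conclusion.** The concern holds as a failure to specify. The only outcome comparison spelled out cannot distinguish ointment from placebo, and the analysis that could do so has no stated terms, contrast or precedence.

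If the paired test were used for efficacy, the false-positive chance would be about 25% to 83% for a shared improvement of 0.3 to 0.8 SD of change, against 5% for a between-arm test. This assumes one test per arm, n = 12 and roughly normal changes. Whether it was so used cannot be told from the document.

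The absence of a ranked outcome is secondary: about 8.5% to 9.5% instead of 5% if either scale may count, for correlations of 0.6 down to 0.2.

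Confidence is high that the specification is missing from this document, and lower about its consequence. It should be corrected before any efficacy statement is relied on.

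**What to change.** 1. Base any efficacy statement on the ointment-versus-placebo contrast from the robust mixed model, for example the difference in change from baseline at week 6. State the response, the fixed and random effects and the contrast. If the fitted model lacks group and group-by-visit terms, refit it with them.
2. Label the paired t-tests as descriptive, and do not infer efficacy from significance in one arm and not the other.
3. Disclose, with its date, any outcome, visit and contrast fixed before outcomes were seen, and list all comparisons made. Do not choose a primary outcome now. If a dated designation ranks the scales, test the second only after the first is significant; if it requires both, each may be tested at the stated level. If nothing was fixed, report both scales with confidence intervals and call the efficacy results exploratory.

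**Cost.** No new data are needed. The work is a dated statement, a list of comparisons, the model specification and one contrast, plus a refit if the terms are absent. The loss is that an effect seen only within one arm could no longer support an efficacy claim. The between-arm contrast is also demanding at this size: about 60% power for an assumed 0.8 SD difference, so a non-significant result should be read from its confidence interval and not as evidence of no effect.
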